3.2 Primary Endpoints

The therapy response assessment based on RANO.

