2.0 OBJECTIVES

2.1. Primary goal

To determine whether the differentiation between pseudo- and true-progressions of glioblastoma can be improved in quantitative DCE-MRI measurement when the P4 phantom is used for error correction.

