2.2. Secondary goal

To determine whether the reproducibility of quantitative DCE-MRI measurement of glioblastoma can be significantly increased when MRI system-driven error is corrected using the P4 phantom.

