The data reproducibility across two different scanners assesses between-scanner variability combined with the inaccuracy of region of interest (ROI), arterial input function (AIF) and image co-registration. The tumor ROI will be determined by [name] (a neuro-radiologist; co-I) (see "ROI determination" section for the details). The ROIs of two scans of each subject will be matched as closely as possible to minimize intra-observer variation. We recently introduced a novel method to reliably measure individualized AIFs (36) which will be employed in this study. If the patient moves during imaging, a similarity transformation (37) will be used for 3D coregistration. The pharmacokinetic (PK) parameters (e.g., K^{trans}) within the ROI will be averaged at each scan after P4-based error correction, and the mean values of two scans will be compared to calculate the reproducibility coefficient (%RDC) using the equation, %RDC=2.77wCV, where wCV is the within-subject coefficient of variation (38). The %RDC before P4-based error correction will also be calculated for comparison. Data reproducibility will be assessed using the intra-class correlation coefficient (ICC) as well. $ICC = \sigma^2 b / (\sigma^2 b + \sigma^2 w)$, where σb is between-subject standard deviation and σw is within-subject standard deviation.

Each tumor will be classified into pseudo- or true-progression based on the histopathologic data or RANO criteria. We expect approximately 40-50% of glioblastoma will be classified to

pseudo-progression, as demonstrated in previous studies (11-13). All PK parameter maps will be created within a month after image acquisition so that the image processing will not be biased by subsequent clinical findings. We will examine whether the difference of tumor PK parameters between pseudo- and true-progressions will become more statistically significant after P4-based error correction.

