8.0 STATISTICAL METHOD

> Sample Size Justification

Aim 1. The K^{trans} reproducibility measured by the ICC was 0.99 in our previous experiment ($\underline{1}$), when the P4 was used for error correction (3 volunteers x 4 tissues = 12 measurements) (see **Fig. 3C**). For brain DCE-MRI, however, the perfusion value can only be assessed in the tumor region. Thus, to achieve greater than 90% power to confirm that the data repeatability measured by the ICC is larger than 0.9 with 5% type I error, at least 12 volunteers will be needed.

Aim 2. In Yun et al's study (13), the difference of tumor K^{trans} between pseudo- and true-progressions was 91% with the standard deviation (SD) of approximately 50% in each group (p=0.004). If the mean and SD of each group in the proposed study will be the same with those of Yun et al's study (0.44±0.25 vs 0.23±0.10 min⁻¹), the sample size (n=12) will have 55% power at a 5% significant level to differentiate the two groups (assuming n=6 per group) using a one-side two-group student t-test. However, if the SD is reduced to ≤35% using the P4, the power will be increased to ≥90%.

> Statistical Analysis

Descriptive analysis with the mean and SD will be presented for each experimental parameter and each time point. Graphic presentation will be considered when appropriate. Due to repeated measurement, ANOVA analysis with a mixed model will be used to estimate the measurement error (within error) with two-sided 95% confidence interval (49). Data

reproducibility will be assessed using both the ICC and %RDC (33). Tumor PK parameters between pseudo- and true-progressions will be compared using two-group student t-test (50). Data will be transformed using natural logarithms if the variability is found to be dependent upon its mean value. All data will be analyzed using SAS (SAS institute, Cary, NC) by [name] (see her support letter).

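### The primary endpoint in Section 3.2 is the RANO reference classification, which P4 correction cannot change, so it cannot answer the primary goal

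*Combined protocol and SAP*

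**What the plan says.** - **Goal.** Section 2.1 asks whether "differentiation between pseudo- and true-progressions of glioblastoma can be improved in quantitative DCE-MRI measurement when the P4 phantom is used for error correction". Section 2.2 makes reproducibility the secondary goal: whether "reproducibility of quantitative DCE-MRI measurement of glioblastoma can be significantly increased when MRI system-driven error is corrected using the P4 phantom".
- **Endpoint.** The whole of Section 3.2 is "The therapy response assessment based on RANO". No other primary endpoint is listed.
- **Role of RANO.** Section 3.1 uses it to label tumours: "Each tumor will be classified into pseudo- or true-progression based on the histopathologic data or RANO criteria".
- **Analysis that involves P4.** Section 3.1 applies the correction to the PK parameters, of which Ktrans is the one given as an example, and adds: "We will examine whether the difference of tumor PK parameters between pseudo- and true-progressions will become more statistically significant after P4-based error correction". It also plans %RDC before and after correction.
- **Test and sample size.** Section 8.0 states: "Tumor PK parameters between pseudo- and true-progressions will be compared using two-group student t-test". Both sample-size arguments there use Ktrans: its ICC for Aim 1 and its group difference for Aim 2.

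**The concern.** A primary endpoint should be a quantity whose value bears on the primary goal. Here the goal is a contrast between corrected and uncorrected measurements, while the endpoint is the grouping against which both sets of measurements are judged. Followed literally, the study would report a primary result that contains no information about P4.

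The analysis that does contain that information has no endpoint status and no effect measure. It is to be judged by whether the group difference gains in significance after correction, which sets two p-values from the same 12 patients side by side. The introduction presents this study as a preliminary test ahead of a larger multi-site trial. That next decision needs an estimate of what P4 adds and how uncertain it is, and the plan does not define one.

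**Working it through.** **1. Does P4 enter the stated endpoint?** Under Section 3.1 each tumour is labelled from histopathology or RANO, and the correction is applied to the PK parameters. Nothing in the document feeds corrected DCE-MRI values into the label. Section 3.1 also has the PK maps made within a month of imaging so that later clinical findings cannot influence them, which keeps the two apart. Each patient therefore has the same label with and without P4, and the corrected-minus-uncorrected difference in the endpoint is zero by definition. Section 3.2 also omits histopathology, so it does not cover the whole reference standard.

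**2. Which quantity was the study sized on?** Inputs from Section 8.0: Ktrans "0.44±0.25 vs 0.23±0.10" per minute, 6 per group, one-sided 5%.
- Difference = 0.44 − 0.23 = 0.21.
- SE = √[(0.25² + 0.10²)/6] = √(0.0725/6) = 0.110.
- Noncentrality = 0.21/0.110 = 1.91; critical t on 10 df = 1.812.
- Power from the noncentral t = 55.3%, against the stated 55%.

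The second figure, at least 90% with an SD of 35% or less, comes out at 86.6% if the SD is 35% of each group's mean, 89.2% if it is 35% of the average mean, and 92.3% on the log scale with a CV of 35%. For Aim 1 (true ICC 0.99 against 0.9, two scans, 12 patients) power is 98.4%, which meets the stated target of over 90%. All these figures concern Ktrans. None uses a RANO outcome, and none is the power to show that separation improves.

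**3. What does a comparison of p-values tell us?** With 6 per group, t = d/√(1/6 + 1/6) = 1.732 d, where d is the standardized group difference (difference divided by pooled SD). A smaller one-sided p after correction therefore means only that d is larger. It shows a direction, without a size or an interval. Suppose the correction merely replaced one set of measurement errors by another of the same size. The corrected and uncorrected d would then be exchangeable, and by symmetry the corrected p would be the smaller in half of such trials.

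**4. How precisely could the improvement be estimated?** Take the scenario in Section 8.0 with the SD reduced to 35% of each mean (0.154 and 0.0805).
- d before = 0.21/√[(0.25² + 0.10²)/2] = 0.21/0.190 = 1.10.
- d after = 0.21/√[(0.154² + 0.0805²)/2] = 0.21/0.123 = 1.71.
- Change = 0.61.
- SE(d) ≈ √(1/6 + 1/6 + d²/24) = 0.620 before and 0.675 after.
- SE(change) = √(0.620² + 0.675² − 2r × 0.620 × 0.675), where r is the correlation between the two estimates. The document does not give r, so I assume 0.5 to 0.9.
- r = 0.5: SE 0.649, 95% half-width 1.96 × 0.649 = 1.27.
- r = 0.9: SE 0.294, half-width 0.58.

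The interval around a change of 0.61 thus extends between about 0.6 and 1.3 either side. This is a large-sample approximation and tends to understate the spread at six per group.

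**5. Would AUC serve better?** The introduction uses AUC (0.76 against a hypothetical 0.99), but Section 8.0 does not. In simulations at 6 versus 6 based on the Section 8.0 means and SDs, a percentile-bootstrap 95% interval for the paired AUC difference excluded zero in about 0.5% to 20% of trials. The low end takes wCV from 20% to 4% with the rest of the SD between patients. The high end is the fivefold SD reduction of the introduction. In roughly 5% to 15% of trials the interval collapsed to zero width. AUC is usable here as a description, not as the quantity that carries the inference.

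**The case against.** The strongest reply is that Section 3.2 is one mislabelled line in an otherwise workable pilot. Sections 3.1 and 8.0 describe the PK comparison and the before-and-after %RDC, no planned analysis uses RANO as an outcome, and the data needed for the primary goal will be collected. In studies of diagnostic measurements the reference outcome is sometimes loosely called the endpoint.

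Much of this stands. A reader might infer that the study cannot address its primary goal at all. The document does not support that: the relevant data and a relevant comparison are both planned. What the reply does not supply is an effect measure. Sections 3.1 and 8.0 never say which quantity expresses improvement, and a gain in significance is not such a quantity.

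Two further inferences are tempting and should not be drawn.
- Because Section 8.0 refers to PK parameters in the plural and names no primary one, a reader might attach a specific inflated false-positive rate. The document does not say how many parameters will be tested or how they correlate, and it states no rule for picking among them, so no rate can be derived.
- A reader might take the order of Aim 1 (reproducibility) and Aim 2 (differentiation) in Section 8.0 as a reversal of primary and secondary. Those aims carry no such label, and their order changes no result.

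**Conclusion.** The point holds. Section 3.2 names the reference classification as the primary endpoint. That classification is unaffected by P4, so it cannot answer Section 2.1. The comparison that could answer it is not an endpoint and is judged by a criterion that shows direction only. This conclusion rests on the text and on no numerical assumption, other than reading Section 3.1 as keeping corrected DCE-MRI values out of the RANO or histopathology label.

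The stated power of 55%, and of at least 90%, should not be read as power for the improvement; both figures belong to the Ktrans group t-test. In the Section 8.0 scenario the improvement itself would be estimated with a 95% half-width of about 0.6 to 1.3 standardized units around a change of 0.61, for an assumed correlation of 0.9 down to 0.5. That is acceptable for a pilot presented as estimation, but it would not support a claim that improvement has been shown.

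**What to change.** - **Primary endpoint (Section 3.2).** Define it as the within-patient, corrected-versus-uncorrected change in how well tumour Ktrans separates true from pseudo-progression, for example the paired change in standardized group difference. State whether Ktrans is the mean of the two scans or comes from one scan named in advance. Report AUC before and after descriptively.
- **Analysis (Sections 3.1 and 8.0).** Report the change as an estimate with a confidence interval, and remove the comparison of significance before and after correction.
- **Reference standard.** State that histopathology or RANO assigns the groups.
- **Secondary endpoint.** wCV/%RDC and ICC before versus after correction, matching Section 2.2.
- **Other PK parameters.** Label them exploratory.
- **Sample size.** Say that the 55% and at-least-90% figures apply to the Ktrans group t-test and not to the before-and-after improvement, and that the interval for the improvement will be wide.

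The cost is a protocol amendment to the wording and one additional paired analysis. No extra patients, scans or data are needed. The drawback is that the primary result becomes an openly imprecise estimate at about six patients per group.

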3.3 Study Duration

Two years.

3.4 Safety and Efficacy Monitoring

This protocol will utilize the University of Alabama at Birmingham O'Neal Comprehensive Cancer Center (CCC) Data and Safety Monitoring Plan. UAB CCC is a National Cancer Institute-designated comprehensive cancer center. Monitoring will be performed by the UAB CCC Clinical Trials Network and Monitoring Office. Serious adverse events will be reported to the chair of CCC Data Safety Monitoring Board (DSMB) within 24 hours of awareness of the event.

3.5 Therapy Modification

Two DCE-MRI imaging will be applied for each participant in addition to his/her standard-of-care. If any adverse is reported in the first DCE-MRI, the second DCE-MRI will not be applied for the participant.

3.6 Ethical Considerations

This study will be conducted in accordance with Good Clinical Practice, the Declaration of Helsinki, and 21CFRPart50 – Protection of Human Patients, Part 56 –Institutional Review Boards, and the other applicable local ethical and legal requirements. The Ethics Review Committee/Institutional Review Board (IRB) must be constituted according to Code of Federal Regulations (CFR).

3.7 Informed Consent

The principles of informed consent in the current edition of the Declaration of Helsinki will be implemented in this study. A written informed consent will be obtained in accordance with 21CFR50.25 and 21CFR50.27 before the protocol – specified procedures are carried out. Participants, their relatives, guardians or, if necessary, legal representatives must be given ample opportunity to inquire about details of the study.

3.8 Confidentiality

Participant names will not be supplied in the data. Only the participant number and initials will be recorded in the case report form (CRF). The participants will be informed that

representatives of the IRB or regulatory authorities may inspect their medical records to verify the information collected, and that all personal information made available for inspection will be handled in the strictest confidence and in accordance with local data protection laws. The investigator will maintain a personal identification list of participants (participant numbers with the corresponding names) to enable records to be identified.

4.0 SELECTION OF PARTICIPANTS

4.1 Number of Participants

We plan to accrue 12 patients at the University of Alabama at Birmingham (UAB). UAB has a total of 11 neurosurgeons for adult patients, seeing about 60 patients with recurrent glioblastoma annually. We presume that at least 16% of them will agree to participate in this study judging from our previous experience in patient enrollment.

4.2 Inclusion Criteria

Patients meeting all the following criteria will be considered for enrollment into the study.

- 1. Adult patients (age 18 years or older).
- 2. Patients with grade 3 or 4 brain tumors treated with surgery, followed by radiotherapy with or without chemotherapy.
- 3. Patients with a newly or enlarged enhancing lesion inside the radiation field.
- 4. Patients with signed informed consent.

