
variation was reduced to about 4% (1). Figure 3 shows the K^{trans} values averaged in each of the four organ regions of three volunteers (n=12) when two different 3T MRI scanners were used (1). Before correction, the ICC between the two data sets was 0.89, and the ICC was not improved by static phantom based error correction (ICC=0.86). However, after P4-based error correction, ICC was increased to 0.99. The P4 is easily operable by MRI technologists, thus it has great potential to facilitate multi-site clinical trials employing quantitative DCE-MRI (qDCE-MRI). Of note, the clinical utility of the P4 was recently demonstrated (34). After P4-based error correction, the change of K^{trans} in pancreatic tumors favorably responding to chemotherapy was able to be significantly differentiated from that in non-responding tumors (p<0.0001) (34). Besides, the P4 was able to improve the accuracy in risk stratification of prostate cancer when assessed by qDCE-MRI (35).

[figure not shown]

Fig. 3. K^{trans} maps before and after correction. K^{trans} averaged in each of the four organs of three volunteers (n=12), when Scanner-A (Y-axis) or Scanner-B (X-axis) was used. (A) before or (B. C) after correction using (B) the static phantom (SP) or (C) P4 (1).

We now hypothesize that the variability in qDCE-MRI measurement of glioblastoma across different scanners will be significantly reduced when MRI system-driven error is corrected using the P4, leading to better differentiation between pseudo- and true-progressions. **Figure 4A**

shows the Gaussian distribution of the K^{trans} value of glioblastoma with true- or pseudo-progression in Yun *et al*'s study (13), where the area under the receiver operator characteristic curve (AUC) was 0.76. **Figure 4B** shows the hypothetical result when the measurement variation is reduced fivefold by our method as demonstrated in **Fig. 3**, increasing the AUC drastically (0.76 vs 0.99). The goal of the proposed study is to conduct the preliminary test of this hypothesis before validating our methodology in an extended multi-site clinical trial (e.g., R01 or U01 study).

[figure not shown]

Fig. 4. Hypothetical Gaussian distribution of glioblastoma K^{trans} values of pseudo- and true-progression groups (A) before and (B) after P4-based error correction.

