3.0 INVESTIGATIONAL PLAN

3.1 Study Design

Figure 5 is a flow chart that illustrates our overall study plan. Each patient will be treated with surgery and followed by radiotherapy with or without chemotherapy. Then standard-of-care brain MRI will be applied every 2~3 months. If a newly or enlarged enhancing lesion is observed in one of the standard-of-care MRI and it is uncertain whether it is pseudo or true-progression, a clinical research coordinator will contact the patient for recruitment. All participants will sign an informed consent form that fully discloses the investigational nature of this study before enrollment. If the patient agrees to participate in this study, a clinical research coordinator will schedule two imaging sessions with the P4 within a one-week period, assuming that the glioblastoma perfusion parameters will not change over a week. The second imaging test will be scheduled at least 24 hours after the first one. Pseudo or true progression of glioblastoma will be determined via histopathologic analysis after biopsy (or surgery) or via the Response Assessment in Neuro-Oncology (RANO) criteria (6). In this pilot study, a

Fig. 5. Overall study plan (TMZ=temozolomide).

total of 12 patients will be recruited. The participants will be at least 18 years old, and will not be pregnant or lactating. Subjects with safety contraindications to MRI examination and those with hemodialysis or acute/chronic renal failure will be excluded. The participants, however, will not be excluded on the basis of race, ethnicity or sex.

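### Section 4.2 admits grade 3 or 4 brain tumours of any histology, but the hypothesis, both goals and the planning values are for glioblastoma, and section 8 defines no glioblastoma analysis set

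*Combined protocol and SAP*

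**What the plan says.** **Eligibility.** Section 4.2, item 2, admits "Patients with grade 3 or 4 brain tumors treated with surgery", followed by radiotherapy with or without chemotherapy. No histology is named. The exclusions in 4.3 concern MRI safety, renal function and reproduction, and none concerns tumour type.

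**Hypothesis and goals.** Section 1.0 hypothesises that "variability in qDCE-MRI measurement of glioblastoma across different scanners will be significantly reduced". The primary goal (2.1) asks whether "differentiation between pseudo- and true-progressions of glioblastoma can be improved", and the secondary goal (2.2) whether "reproducibility of quantitative DCE-MRI measurement of glioblastoma can be significantly increased".

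**Design.** Section 3.1 places both scans within a week, "assuming that the glioblastoma perfusion parameters will not change over a week". On the outcome label it says: "Pseudo or true progression of glioblastoma will be determined via histopathologic analysis after biopsy" or surgery, or through the RANO criteria. On the expected split it says: "We expect approximately 40-50% of glioblastoma will be classified to" pseudo-progression.

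**Accrual and sample size.** Section 4.1 plans 12 patients and bases this on about 60 recurrent glioblastoma patients seen each year, of whom at least 16% are presumed to agree. The Aim 2 means and SDs in section 8 come from reference 13, whose title names glioblastoma.

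**Analysis.** Section 8 compares tumour pharmacokinetic parameters between the two progression groups with a two-group t-test, and assesses reproducibility by ICC and %RDC. It defines no glioblastoma set, does not stratify by grade or histology, and has no rule for other tumours.

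**The concern.** The people the criteria let in are not the people the goals describe. A coordinator who screens against 4.2 could enrol a patient whose tumour is not glioblastoma, and nothing in section 8 would keep that patient out of the t-test or the reproducibility estimates. With 12 patients, each one is 1/12, or about 8%, of the sample.

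Two things are at stake. The first is interpretation: a result from a mixed sample would be reported against goals that speak only of glioblastoma, and it is meant to inform a larger multi-site trial of the same hypothesis. The second is the planning: the Aim 2 power rests on glioblastoma means and SDs and does not automatically carry over to a wider population.

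**Working it through.** **1. Population named in each place**

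| Place | Population |
|---|---|
| 1.0, hypothesis | glioblastoma |
| 2.1 and 2.2, goals | glioblastoma |
| 3.1, one-week stability, classification, expected share | glioblastoma |
| 4.1, accrual base | recurrent glioblastoma |
| 4.2, item 2 | grade 3 or 4 brain tumour, no histology |
| 4.3, exclusions | no limit by tumour type |
| 8.0, source of Aim 2 values | glioblastoma (title of reference 13) |
| 8.0, analysis | tumour parameters, no set defined |

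Only 4.2 is wider, and no passage links the two populations.

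**2. The plan's own power figure**

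Inputs from section 8: means 0.44 and 0.23, SDs 0.25 and 0.10, 6 per group, one-sided two-group t-test at 5%.

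- Difference: 0.44 − 0.23 = 0.21.
- Pooled SD: √((0.25² + 0.10²)/2) = √0.03625 = 0.190.
- Standard error: 0.190 × √(2/6) = 0.110.
- Noncentrality: 0.21/0.110 = 1.91, with 10 degrees of freedom and critical value 1.812.
- Power from the noncentral t distribution: 55.3%.

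The stated 55% is reproduced. It describes 12 patients drawn from the population of reference 13.

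**3. What pooling would do to it**

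This needs the share of other tumours among the 12 and their Ktrans means and SDs in each progression group. The documents give none of these. Any figure would be invented, so none is offered.

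**4. What a glioblastoma-only set would cost if enrolment stopped at 12**

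The calculation is as in step 2, with equal groups and the stated SDs. The counts of 10 and 8 are assumptions for illustration.

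| Glioblastoma patients | Per group | Standard error | Noncentrality | df | Critical t | Power |
|---|---|---|---|---|---|---|
| 12 | 6 | 0.110 | 1.91 | 10 | 1.812 | 55% |
| 10 | 5 | 0.120 | 1.74 | 8 | 1.860 | 48% |
| 8 | 4 | 0.135 | 1.56 | 6 | 1.943 | 40% |

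These are powers of the single group comparison in section 8, not of the before/after improvement named in goal 2.1.

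**5. Accrual if 4.2 were limited to glioblastoma**

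Inputs: 60 patients a year and 16% (4.1), two years (3.3).

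- 60 × 0.16 = 9.6 a year, or 19.2 in two years, against 12 needed.
- 12/9.6 = 1.25 years, or 15 months, to reach 12.
- 12/19.2 = 62.5%: the fraction of the projected patients who must also meet the lesion criteria if recruitment ran for the full two years.

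The 16% is stated as a minimum. The 60 is counted before the lesion criteria are applied, and the two years must also hold imaging and classification. The margin may therefore be smaller than 19.2 suggests.

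**The case against.** The best defence is that the wider criterion is deliberate and the word glioblastoma is used loosely elsewhere. There is some support for this. RANO, one of the two classification routes, is cited to a paper whose title covers high-grade gliomas (reference 6), and one of the three sources for the expected share has glioma in its title (reference 11). This shows that the tools could serve a wider population. It does not change the goals, which name glioblastoma. If the wider criterion was intended, the goals and planning values were not carried across to match it.

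A second defence is that accrual in 4.1 draws only on glioblastoma patients, and that 4.2 says only that patients meeting its criteria may be considered. Enrolment of other tumours is therefore possible, not shown to be planned. That is fair, and it limits the weight of the point. But 4.2 is the eligibility list, and nothing else in the plan would stop such enrolment.

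A third is that this is a 12-patient pilot and no bias has been demonstrated. That is correct, and the conclusion is limited accordingly. A pilot meant to test a glioblastoma hypothesis still has to say whose data test it.

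**Conclusion.** The eligibility text and the stated study population contradict each other, and section 8 does not resolve the difference. This should be corrected before enrolment. Confidence in the mismatch is high. Its effect on the results is not quantifiable from the documents.

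A reader might infer more than this, and three such readings are not supported:

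- **That the 55% is wrong.** It reproduces. It is conditional on all 12 patients having glioblastoma, or on other tumours sharing the same means and SDs.
- **That pooling would lower power or bias the comparison by a known amount.** Size and direction are both unknown. The 48% and 40% above are the price of leaving patients out of the set, not a measure of pooling.
- **That goal 2.2 loses its power.** For the section 8 test of ICC 0.99 against 0.9, with two scans and one-sided 5%, the F test with n − 1 and n degrees of freedom and ratios (1 + ICC)/(1 − ICC) of 199 and 19 gives 98% for 12 patients, 96% for 10 and 92% for 8. All exceed the 90% target. For 2.2 the issue is only which population the result describes.

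**What to change.** Reconcile the passages before enrolment by one of three routes. The choice is the sponsor's.

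- **(a) Limit item 2 of 4.2 to glioblastoma.** This matches the goals, the planning values and the accrual base. The cost is a narrower pool than 4.2 now allows, with the accrual margin uncertain as shown above.
- **(b) Keep 4.2 and define in section 8 a glioblastoma set on which goals 2.1 and 2.2 are assessed.** Report other tumours separately, and state whether the 12 in 4.1 counts glioblastoma patients only. No patient is turned away, but the set falls below 12 unless enrolment continues until 12 glioblastoma patients are in.
- **(c) Restate the hypothesis and goals, with the matching text in 3.1, for grade 3-4 tumours.** Note in section 8 that the Aim 2 planning values come from glioblastoma only. There is no accrual cost, but the conclusion is no longer specific to glioblastoma and the 55% may not apply to the wider population.

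All three are wording amendments. None adds a scan or a procedure for a participant.
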